## **date of the document:**

**9 May 2022**

## The Research Plan

### 1 Research Background

Chronic obstructive pulmonary disease (COPD) is the fourth leading cause of death globally, affecting up to 14% of individuals over 65 years old. This results in a significant burden on healthcare systems and the global economy, with the economic cost of COPD projected to exceed \$4.3 trillion by 2050^2. Persistent hypoxemia and systemic inflammation in COPD have been shown to accelerate lung function decline. Additionally, accumulating evidence suggests these factors may contribute to cognitive impairment through hypoxia-induced neuronal damage. COPD has been identified as an independent risk factor for cognitive impairment, with disease duration correlating directly with an increased risk of developing mild cognitive impairment (MCI). Research indicates that 25% of COPD patients experience MCI, a rate notably higher than the 13% prevalence in the general population. MCI, a precursor to dementia, is characterized by executive dysfunction, memory deficits, and impairments in attention, orientation, and executive function. These cognitive deficits significantly affect the self-management capabilities of elderly COPD patients with MCI, influencing medication adherence and long-term oxygen therapy (LTOT) compliance. As a result, a detrimental cycle of hypoxemia and cognitive decline may be perpetuated.

LTOT, when administered for at least 15 hours daily, has been shown to significantly improve blood oxygen levels in elderly COPD patients with MCI. This

---

 Yohannes, A. M., Chen, W., Moga, A. M., Leroi, I., & Connolly, M. J. (2017). Cognitive Impairment in Chronic Obstructive Pulmonary Disease and Chronic Heart Failure: A Systematic Review and Meta-analysis of Observational Studies. *Journal of the American Medical Directors Association*, 18(5), 451.e1–451.e11.

therapy effectively alleviates cognitive impairment, particularly in memory and attention, and may partially enhance comfort, exercise tolerance, and sleep quality. However, adherence to LTOT remains suboptimal due to insufficient awareness of its benefits. Health education interventions are essential for enhancing patient knowledge and improving COPD management. Nurse-led educational interventions have been shown to provide personalized information, engage patients in decision-making, and improve treatment adherence and health outcomes. These interventions are also costeffective. However, existing research typically focuses on a single condition (COPD or MCI) and neglects the interactions between co-morbidities. Additionally, many studies rely on "one-way" educational methods, such as brochure distribution, which are not grounded in behavioral change theories and fail to address cognitive-behavioral factors influencing LTOT adherence in MCI patients. Consequently, the impact of these interventions is often short-lived. Furthermore, contemporary educational interventions, grounded in traditional theoretical frameworks (e.g., health beliefs theory, knowledge-attitude-behavior theory), improve health behaviors and literacy but often overlook participants' physical and mental capabilities, including their ability to monitor health effectively.

---

 Michael Doherty, Wendy Jenkins, Hugh H. Richardson, Aliya Sarmanova, Abhishek Abhishek, Deborah Ashton, Christine Barclay, Sally Doherty, Lelia Duley, Rachael Hatton, Frances Rees, M Stevenson, & Weiya Zhang (2018). Efficacy and cost-effectiveness of nurse-led care involving education and engagement of patients and a treat-to-target urate-lowering strategy versus usual care for gout: a randomised controlled trial. *The Lancet*, 392 (10156), 1403-1412.

 Baker, E., & Fatoye, F. (2017). Clinical and cost effectiveness of nurse-led self-management interventions for patients with copd in primary care: A systematic review. *International journal of nursing studies*, 71, 125–138.

## **2. Research Objectives**

1. To investigate the problems and self - care needs of elderly COPD patients with MCI in using home oxygen concentrators.
2. To apply the BCW theory model to construct a health education model and explore its application effect in improving the self - management ability and compliance of elderly patients with MCI and COPD during long - term oxygen therapy with home oxygen concentrators.

## **3. Research Method**

---

### **3.1 Object of Study**

1. **Source of the study subjects and the sampling methods:** The study subjects will be selected from the respiratory department of a tertiary hospital in Xiamen, Fujian Province, and a community health service center in Tong'an District, Xiamen. The sampling method is convenience sampling.
2. **Inclusion criteria for the study subjects:**
  - Diagnosed as COPD by a physician.
  - $\text{SpO}_2 < 88\%$  or  $\text{PaO}_2 < 60\text{mmHg}$ .
  - Diagnosed with MCI.
  - Have a home oxygen concentrator.
  - No communication barriers.
3. **Exclusion criteria for the study subject:**
  - Complicated with asthma or lung cancer.
  - Long - term home oxygen therapy time  $\geq 15\text{h/d}$ .
  - Participated in similar interventions.
4. **Samplesize estimation:** The sample size is calculated using the formula for comparing two - sample rates. Referring to the literature, the oxygen therapy compliance rate is 20%, and it is expected to increase by 40% after intervention. With a significance level of 0.05 and a Type II error probability of 0.1, 32 cases are required for each of the intervention group and the control group. Considering a 20% dropout rate, the final sample size is determined to be 39 cases per group, with a total of 78 cases.

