### **3.3 Data Processing and Statistical Analysis**

1. After the data collection is completed, SPSS 20.0 software is used for statistical analysis.
2. The description of general demographic data and clinical data: Count data are described by frequency and percentage; measurement data are described by median.
3. Comparison of general demographic data and clinical data between the two groups of research subjects: Rank - sum test and X test are used.
4. Comparison of the total scores of long - term home oxygen therapy beliefs at each time point between the two groups of research subjects: Repeated - measures analysis of variance is used.
5. Comparison of the scores of each dimension of long - term home oxygen therapy beliefs, long - term home oxygen therapy behavior scores, and average daily oxygen inhalation time at each time point between the two groups of research subjects: Generalized linear mixed - effect model is used for analysis.
6. Comparison between groups of the total scores and scores of each dimension of long - term home oxygen therapy beliefs, long - term home oxygen therapy behavior scores, and average daily oxygen inhalation time at different time points of the two groups of research subjects: If it conforms to the normal

---

distribution, an independent - sample t - test is used; if it does not conform to the normal distribution, a two - independent - sample rank - sum test is used.

7. Comparison within groups of the total scores and scores of each dimension of long - term home oxygen therapy beliefs, long - term home oxygen therapy behavior scores, and average daily oxygen inhalation time at different time points of the two groups of research subjects: If it conforms to the normal distribution, a paired t - test is used; if it does not conform to the normal distribution, a paired rank - sum test is used.
8. Comparison of the differences in the scores of the Montreal Cognitive Assessment Scale, Mini - Mental State Examination, Geriatric Depression Scale, and Self - rating Anxiety Scale between the intervention group and the control group: An independent - sample t - test is used.

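### The plan does not say how patients are assigned to intervention or control, and no analysis adjusts for recruitment site or a baseline covariate

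*Combined protocol and SAP*

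**What the plan says.** Section 3.1, item 1, names the source of patients as "the respiratory department of a tertiary hospital in Xiamen, Fujian Province, and a community health service center in Tong'an District, Xiamen", and adds that "The sampling method is convenience sampling". Item 4 of the same section sets up a two-group comparison: "32 cases are required for each of the intervention group and the control group", raised to 39 per group and 78 in total for dropout.

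The supplied text contains no assignment step: no random sequence, concealment, stratification, matching, or assignment by site or calendar period. Randomisation is mentioned only in the titles of cited papers. Section 3.4, item 4, asks that both groups follow the design plan, but gives no rule for forming them.

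Section 3.3 handles the groups as follows:
- Item 3 is a "Comparison of general demographic data and clinical data between the two groups of research subjects", by rank-sum and chi-square tests. It does not say what follows from a difference.
- Item 4 (repeated-measures analysis of variance) and item 5 (generalised linear mixed model) compare the groups across time points. Neither lists a site term or a covariate.
- Item 6 compares the groups at each time point by t-test or rank-sum test, unadjusted.
- Item 7 makes paired comparisons within each group.
- Item 8 compares cognitive, depression and anxiety scales between groups by t-test, unadjusted.

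**The concern.** Objective 2 asks a causal question: what the education model does for self-management and compliance. That needs groups that differ only by chance, or an analysis that accounts for how they differ.

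Three features combine here. The assignment method is unstated. The two settings could plausibly differ in severity, cognition, readiness to change and follow-up contact. No analysis names site. A team following the text literally could give the education to patients who seem more willing, or run it mainly at one site, without departing from the plan. Daily oxygen time is self-reported and the behaviour survey is self-designed (section 3.2), so a difference in motivation between groups would feed straight into the outcomes. A reader of the results could not tell whether this was a randomised trial.

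**Working it through.** **1. The plan's own figure.** Inputs from 3.1, item 4: "the oxygen therapy compliance rate is 20%, and it is expected to increase by 40% after intervention", read as 20% to 60%; alpha 0.05, taken as two-sided; type II error 0.1. With mean rate 0.40 and difference 0.40:

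n = 2 × 0.40 × 0.60 × (1.960 + 1.282)² / 0.40² = 0.48 × 10.507 / 0.16 = 31.5, so 32 per group.

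Dropout: 32 × 1.2 = 38.4, so 39. Both figures reproduce. The formula assumes two comparable groups of equal size. Random 1:1 allocation would supply that at the same sample size.

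**2. What the planned analyses can and cannot remove.**

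| 3.3 item | Stable baseline gap between groups | Different trend by site |
|---|---|---|
| 3 (baseline tests) | may detect it, does not remove it | no |
| 4, 5 (repeated measures) | removed if baseline is a time point and the group-by-time term is the test; neither is stated | no |
| 6 (each time point) | not removed | no |
| 7 (within group) | not a between-group comparison | no |
| 8 (scales) | no adjustment named | no |

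**3. How far item 3 can reassure.** Item 3 names rank-sum and chi-square tests. As an approximation, take a two-sided t-test at 39 per group (76 degrees of freedom, noncentrality d × √(39/2)):
- imbalance of 0.3 SD: noncentrality 1.32, power 25.8%
- imbalance of 0.5 SD: noncentrality 2.21, power 58.7%

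A non-significant baseline test is therefore weak evidence of comparability.

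**4. Illustration of size.** The documents give no rates by site, so the site rates below are assumptions, chosen to average the plan's 20%. The test is an uncorrected chi-square on compliance, which 3.3 does not list; compliance rate appears only in the sample-size calculation. There is no true effect and 32 per group are analysed. Each group's rate is a site-mix average, p = w × pA + (1 − w) × pB. For example, with site rates of 30% and 10% and a 75:25 v 25:75 mix, the group rates are 0.75 × 0.30 + 0.25 × 0.10 = 0.25 and 0.25 × 0.30 + 0.75 × 0.10 = 0.15. Exact enumeration of both binomials gives:

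| Site rates | Site mix in the two groups | Group rates | False positives |
|---|---|---|---|
| no gap | any | 20% v 20% | 5.1% |
| 25% v 15% | 75:25 v 25:75 | 22.5% v 17.5% | 7.9% |
| 25% v 15% | one site per group | 25% v 15% | 16.9% |
| 30% v 10% | 75:25 v 25:75 | 25% v 15% | 16.9% |
| 30% v 10% | one site per group | 30% v 10% | 53.2% |

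In the one-site-per-group rows, site and treatment are the same variable. A site term could not then be separated from the treatment effect, so adjustment would not help. Only allocation within sites rules that case out.

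**The case against.** The strongest reply is that convenience sampling says how patients are found, not how they are divided. It mainly limits generalisability and is compatible with randomising everyone who is recruited. That stands. A reader might infer from 3.1 that the trial is non-randomised, or that one setting serves as control for the other. The documents say neither. What they support is that the method is unstated. The title page is not in the supplied text and might carry a design label, but a label would not supply a procedure.

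A reader might also infer that the item 3 tests are the only protection. They are not. Items 4 and 5 can remove stable baseline differences under the conditions in the working. Section 3.1 also applies the same oxygenation limits at both sites and excludes anyone already at 15 hours a day or more. If compliance means that threshold, everyone enters non-compliant and baseline compliance cannot differ by site. These points narrow the concern. They do not cover different trends by site, or the unadjusted tests in items 6 and 8.

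Finally, the illustration rests on assumed rates and on a test the analysis plan does not list, and its mildest case is 8% against a nominal 5%. That is also correct, so it shows direction and range and does not estimate this trial's bias.

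**Conclusion.** The point holds as an omission with consequences for the causal claim. The assignment method is not stated, two settings are used, and no analysis names site or a baseline covariate. Followed as written, the plan cannot secure the inference that objective 2 needs.

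Confounding is possible, not shown. That the settings differ is plausible but not documented. The illustrative range, about 8% to 53% false positives, depends on the assumed site rates, the assumed site mix, 32 per group and a chi-square test of compliance. Its upper end needs both a 20-point site gap and complete alignment of site with group, for which the documents give no evidence. A reader might also conclude that this is the largest bias in the trial. Nothing in the documents allows that ranking.

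This should be corrected, because the remedy is specific and cheap and the interpretation of every between-group result depends on it.

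**What to change.** **Section 3.1.** State that, after consent and baseline assessment, patients are allocated 1:1 by a computer-generated random list concealed from those who recruit. Stratify by site if practicable. Simple randomisation would also be valid; stratifying keeps the sites balanced at this size.

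**Section 3.3.** Base the between-group comparisons in items 4, 5, 6 and 8 on models that include site and the baseline value of the outcome, whatever the item 3 p-values are. A site term in item 5 alone would leave items 4, 6 and 8 unadjusted. Say whether baseline is a time point in items 4 and 5 and name the term that tests the education effect.

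**If groups are formed without randomisation.** Say so, describe how, prespecify the same adjustment and report the result as an association. Both groups must then be recruited at both sites, or the site term cannot be estimated apart from treatment.

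**Cost.** Protocol wording, one allocation list and one or two model terms. The sample size stays at 39 per group.

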### 3.2 Research Tool

(1) The execution of LTHOT was assessed using a self-designed Long-Term Home Oxygen Therapy Behavior Survey. Given that improper operational skills can affect the effectiveness of long-term home oxygen therapy, the survey primarily includes four dimensions: adherence to home oxygen therapy, cleaning and disinfection, safe oxygen use, and self-monitoring, with a total of 13 items. Each item has two response options: "Yes" and "No," where "Yes" indicates the behavior was performed, and "No" indicates it was not. A score of 1 is awarded for "Yes," and 0 for "No." The higher the total score, the better the patient's long-term home oxygen therapy behavior. The average daily oxygen use time was self-reported by the patient.

(2) LTHOT Health Belief was assessed using the Long-Term Home Oxygen Therapy Health Belief Questionnaire designed by Yan, J. The questionnaire consists of four dimensions and 26 items. Scores are based on the individual's understanding of their ability to engage in long-term home oxygen therapy behaviors. The total score ranges from 0 to 104, with higher scores indicating a higher level of perceived ability to perform long-term home oxygen therapy health behaviors.

(3) Activity of Daily Living (ADL): Daily living ability was assessed using the Activity of Daily Living scale, with a total score range of 14-56 points. A higher score indicates poorer functional ability. A total score greater than 16 points indicates varying degrees of functional impairment, while a score of 22 points or higher indicates significant functional impairment. If the score for any single item exceeds 3 points, or if two or more items score over 3 points, this suggests significant functional impairment.

(4) Ventilation Function Indicators: These include blood oxygen saturation (SpO2), arterial carbon dioxide partial pressure (PaCO2), arterial oxygen partial

---

pressure (PaO2), pH, lung function (FEV1%), dyspnea score, and 6-minute walk distance (6MWD).

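### The trial is sized to compare two compliance rates (20% vs 60%, 90% power), but section 3.3 lists no comparison of a compliance proportion, so the stated power belongs to no listed test

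*Combined protocol and SAP*

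**What the plan says.** **Sizing (3.1 Object of Study, item 4).** The method is given as "The sample size is calculated using the formula for comparing two - sample rates", and the inputs as "Referring to the literature, the oxygen therapy compliance rate is 20%, and it is expected to increase by 40% after intervention". The significance level is 0.05 and the type II error 0.1. The result is 32 per group, raised to 39 per group (78 in total) for 20% dropout.

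**Measurement (3.2 Research Tool, item 1).** Oxygen-therapy behaviour is measured by a yes/no survey covering "adherence to home oxygen therapy, cleaning and disinfection, safe oxygen use, and self-monitoring, with a total of 13 items". Daily hours are recorded separately: "The average daily oxygen use time was self-reported by the patient". Neither measure is given a cut-off for being compliant.

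**Analysis (3.3 Data Processing and Statistical Analysis).** There are eight items:

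- Items 1 and 2 cover software and description.
- Item 3 holds the only chi-square test, for "Comparison of general demographic data and clinical data between the two groups of research subjects".
- Item 4 is the total belief score, by repeated-measures ANOVA.
- Item 5 covers belief dimensions, behaviour scores and "average daily oxygen inhalation time at each time point between the two groups of research subjects"; the method is stated as "Generalized linear mixed - effect model is used for analysis".
- Item 6 adds between-group tests of the belief, behaviour and hours variables at different time points: under normality "an independent - sample t - test is used; if it does not conform to the normal distribution", a rank-sum test.
- Item 7 gives the within-group versions.
- Item 8 covers cognitive, depression and anxiety scores, by t-test.

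**The concern.** A power statement has meaning only for a particular test of a particular endpoint. Here it is worked out for a binary endpoint, compliant or not, while the analysis section handles adherence only as a score and as a number of hours. Followed as written, section 3.3 never runs the test for which 90% power was calculated, and the plan gives no SD or difference from which the power of the tests it does list could be found.

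The link is not supplied elsewhere. The visible text labels no outcome as primary, refers to several time points without naming them, and does not say what counts as compliant. Several adherence-related results, at several times and by more than one method, could therefore each be put forward as the main finding, and nothing in section 3.3 says which one the sample size was meant to support.

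**Working it through.** **1. Reproduce the stated sample size.** Inputs from 3.1, item 4: p1 = 0.20; p2 = 0.60 (reading the increase as 40 percentage points); alpha 0.05, taken as two-sided because sidedness is not stated; power 0.90. Mean rate 0.40.

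n per group = 2 × 0.40 × 0.60 × (1.960 + 1.282)² / 0.40² = 31.5, so 32. This matches.

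A relative reading (20% to 28%) would need about 594 to 599 per group, depending on the formula, so the plan must mean 20% against 60%.

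Dropout: 32 × 1.2 = 38.4, so 39. This also matches. Completers at 20% loss: 39 × 0.8 = 31.2, so 31 per group.

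**2. Look for the sized comparison in 3.3.** Going through the eight items, none takes a compliance proportion as its outcome. Item 3 is the only place where proportions are tested, and it covers the same general demographic and clinical data that item 2 describes. The oxygen-therapy outcomes are listed separately, in items 4 to 7, as scores and hours.

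**3. Power if the sized comparison were run.** Exact enumeration over two binomials, 31 per group, 20% vs 60%, two-sided 0.05:

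| Test | Power |
|---|---|
| Chi-square, no continuity correction | 0.918 |
| Chi-square, continuity correction | 0.867 |
| Fisher exact | 0.870 |

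**4. Power of the nearest listed test, the item 6 t-test on hours, 31 per group.**

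- *With a link to the sizing assumption (assumed).* If compliance is a cut-off on hours that are normal with equal SD in both groups, 20% vs 60% corresponds to a shift of z(0.60) − z(0.20) = 0.253 + 0.842 = 1.095 SD. The non-centrality is 1.095 × √(31/2) = 4.31 on 60 degrees of freedom, and power is 0.989.
- *Without that link.* The test reaches 90% power at a difference of 0.84 SD. The plan gives no SD or difference in hours to set against this.

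**5. Dependence on the definition.** Section 3.1, item 3 excludes patients already using oxygen for 15 hours a day or more. If that figure were also the compliance definition (the documents do not say so), nobody would be compliant at entry, and 20% could only be a control rate at follow-up. For assumed control and intervention rates with 31 per group, power is 0.981 for 5% vs 45% and 0.792 for 5% vs 30%. The stated power cannot be confirmed until the definition is written down.

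**The case against.** **Hours are a reasonable measure of adherence, and they are tested between groups.** Sizing on a rate and then analysing the underlying continuous measure is usually conservative. This stands as far as it goes. A reader might infer from the mismatch that the trial is underpowered, and the documents do not support that: under the cut-off assumption the listed t-test does better than 90%. But that result rests on an hours threshold and a normal distribution that the plan never states, so it cannot take the place of a stated link.

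**The plan does show what it is mainly about.** The last paragraph of section 1 puts implementation of long-term oxygen therapy first, with adherence heading the targeted behaviours, ahead of beliefs, cognition, ventilation and daily living. Objective 2 names compliance, and the sizing uses it. This also stands. A reader might infer that the plan gives no sign of its main question, which goes too far. What is missing is the formal label, the definition and the time point.

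**Item 3 or item 5 might be stretched to cover compliance.** A compliance rate could be called clinical data, and a generalized mixed model can take a binary outcome. Neither use is stated. Item 3 follows the descriptive data of item 2, item 5 names scores and hours, and no binary variable is defined for either to analyse.

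**Some material was removed before review.** A primary outcome might have been named there, so that part of the point is limited to the visible text. The absence of a compliance test from section 3.3 is not affected, because its items can be read in full.

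**Conclusion.** The point holds as a mismatch between sizing and analysis. The sample size arithmetic is sound: 32 and 39 per group both reproduce. The 90% power applies to a two-proportion test of compliance that section 3.3 does not list, and the plan lacks the inputs to give a power for the adherence analyses that it does list.

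No loss of power is shown. Depending on how the gap is closed, power with 31 completers per group is about 92% (87% with continuity correction) for the sized comparison, or about 99% for a t-test on hours if compliance is a cut-off on normally distributed hours. The first figure assumes the plan's own 20% and 60%; the second adds the distributional assumption. Neither supports a claim that 78 patients are too few.

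It is still worth correcting as more than missing detail, because a team that followed section 3.3 exactly would never carry out the comparison for which the trial was sized.

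**What to change.** In section 3.3, add one primary analysis: the between-group difference in the proportion compliant at one stated follow-up time point, with a 95% confidence interval and a two-sided chi-square test at 0.05. State whether a continuity correction is used, since it moves the power between 92% and 87%. Define compliance as in the source of the 20% rate, and label all other outcomes and time points secondary. The existing 39 per group then stands. If the definition turns out to be 15 hours a day or more, justify 20% as a control rate at follow-up given the exclusion in 3.1, or restate the power.

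Alternatively, make average daily oxygen hours at that time point primary, name the single test or model to be used, give an assumed SD and difference, and restate the power for 78 patients. The choice between the two, and the definition itself, rest with the investigators.

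The cost is wording in 3.1 and 3.3, plus at most one extra comparison from data already being collected; no patients or visits are added. The downsides are small: the stated power may change, and secondary scores can no longer be presented as the main result.

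### At the plan's own 20% dropout, 39 per group leaves about 31, one short of the 32 it requires; 40 would keep 32

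*Combined protocol and SAP*

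**What the plan says.** Everything relevant is in section 3.1 (Object of Study), item 4, of the combined protocol and SAP. The trial is sized on a comparison of two rates.

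- Rates: "the oxygen therapy compliance rate is 20%, and it is expected to increase by 40% after intervention".
- Error rates: "With a significance level of 0.05 and a Type II error probability of 0.1".
- Requirement before dropout: "32 cases are required for each of the intervention group and the control group".
- Enrolment after the dropout allowance: "Considering a 20% dropout rate, the final sample size is determined to be 39 cases per group, with a total of 78 cases".

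The item does not show how the dropout allowance was applied, and it does not say whether the test is one-sided or two-sided. No other section restates or corrects these numbers.

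**The concern.** A dropout allowance is meant to ensure that, after the expected losses, the required number of patients is still available. A dropout rate is ordinarily a share of those enrolled, so the requirement is divided by one minus the rate. Here 39 is below that result, and the expected number remaining falls just under the plan's own target.

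What is at stake is the internal consistency of the only sample size statement in the document. A reader will take it to mean that 39 per group fully covers 20% dropout, and it does not. The stakes for power are slight.

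**Working it through.** **Inputs, all from section 3.1, item 4:** 32 required per group; 20% dropout; 39 enrolled per group (78 in total); 20% compliance, expected to rise by 40%; significance level 0.05; Type II error 0.1, so 90% power.

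**Assumptions, needed only for the power figures:** the rise is 40 percentage points (20% against 60%), and the test is two-sided.

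**1. Reproducing the 32.** With the pooled variance in both terms, n = 2·p̄(1 − p̄)(z_α + z_β)²/d², where p̄ = 0.4 and d = 0.4:

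2 × 0.4 × 0.6 × (1.960 + 1.282)² / 0.4² = 31.52, rounded up to 32.

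This matches the plan. Reading the rise as relative (20% to 28%), or as a rise to 40%, gives far larger numbers: at least 485 − 1 = 484 and 86 per group respectively, even one-sided. The 20% against 60% reading is therefore the one that fits.

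**2. The dropout step.**

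- Expected to remain: 39 × 0.8 = 31.2 per group, which is 32 − 31.2 = 0.8 short.
- Both groups: 78 × 0.8 = 62.4, against 2 × 32 = 64.
- Enrolment that keeps 32: 32/0.8 = 40 per group, 80 in total.
- Losses 39 can absorb: 39 − 32 = 7, and 7/39 = 17.9%. An eighth loss (8/39 = 20.5%) leaves 31. Expected losses at 20% are 39 × 0.2 = 7.8.

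This step starts from the plan's own 32, so it depends neither on how the effect is read nor on whether the test is one- or two-sided.

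**3. How 39 may have arisen (inference only).**

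- 32 × 1.2 = 38.4, rounded up to 39.
- 31.52/0.8 = 39.40, rounded to the nearest whole number, 39.

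On either route 39 leaves 31.2 at 20% dropout. That is 0.8 below 32 and 31.52 − 31.2 = 0.32 below the unrounded requirement. Measured against 31.52, a group of 39 can absorb 1 − 31.52/39 = 19.2%.

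**4. Effect on power (20% against 60%, two-sided 0.05).**

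| Per group | Simple pooled formula | Pooled/unpooled formula |
|---|---|---|
| 31 | 89.5% | 91.5% |
| 31.2 | 89.7% | 91.7% |
| 32 | 90.4% | 92.4% |

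Simple pooled: power = Φ(d·√(n/(2p̄(1 − p̄))) − 1.960). At n = 31 this is Φ(0.4 × √(31/0.48) − 1.960) = Φ(1.255) = 89.5%.

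Pooled/unpooled: power = Φ((d√n − 1.960·√(2p̄(1 − p̄)))/√(p₁(1 − p₁) + p₂(1 − p₂))). At n = 31 this is Φ((2.227 − 1.358)/0.632) = 91.5%.

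Exact enumeration for the uncorrected chi-square test gives 91.8% at 31 and 93.0% at 32.

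**The case against.** The strongest reply is that the plan never defines its allowance. Adding 20% to 32 gives 38.4, hence 39, and on that convention the figures agree with each other. This plausibly explains how 39 came about, but it does not make 39 sufficient: if 20% of those enrolled are lost, fewer than 32 remain.

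The second reply is that nothing practical follows, and this largely stands. Power falls below 90% only under the more conservative formula that reproduces 32, and then by half a point; the other two methods stay above 90% at 31 per group. A gap of one patient is also within the difference between acceptable sample size formulas. That tolerance concerns the choice of formula, however, whereas the question here is whether the allowance meets the plan's own stated target.

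It is also fair to say that the power figures rest on assumptions the plan does not state, and that section 3.3 lists no between-group comparison of compliance rates. One patient more or fewer for a two-rate test therefore bears little on the analyses actually listed. Both points limit the weight of the finding without removing the shortfall.

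**Conclusion.** The concern holds, as a minor point. Enrolling 39 per group does not deliver the stated 32 at the stated 20% dropout; it does so only up to 17.9%. Confidence in the shortfall is high, because it follows from three numbers in one paragraph. How 39 was obtained remains inference.

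The loss of power between 32 and 31 per group is about one percentage point or less by the two formulas in the table (0.9 point each), conditional on 20% against 60% and a two-sided test. Neither the design nor any conclusion of the trial is affected.

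**What to change.** Restate the figure in section 3.1, item 4, in one of two ways:

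- 39 per group keeps 32 evaluable patients if dropout is at most 17.9% (7 of 39). This needs no power calculation.
- At 20% dropout about 31 per group remain, with power of about 89.5% by the simple pooled two-proportion formula, for 20% against 60% and a two-sided 0.05 level.

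Either costs one sentence and works whether or not enrolment has closed. Enrolling 40 per group would also reconcile the numbers, at two more patients in total, but the shortfall is too small to require it.
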